#### Proximal Outcomes: Sibling Behavior & Adults with ASD (Timing indicated below)

1. **Sibling Plan of Action (T2)**. Siblings will submit a written plan of action at the final session; control participants will complete this plan at Time 2. We will use a template on which siblings will detail their short- and long-term goals with respect to family future planning and concrete next steps. Researchers will rate each plan according to the following criteria: (1) inclusion of short- and long-term goals and next steps, (2) appropriate scope of next steps, (3) alignment with the needs and/or preferences of the adult with ASD, (4) accuracy (e.g., are they identifying the right resources to meet the identified goal?), and (5) sufficient detail (e.g., including the names and phone numbers of actual resources vs. making vague plans). At the 3-month follow up time point, we will assess whether or not the sibling attempted or achieved their primary short-term goal, the steps they took to achieve their goal, and concrete outcomes of the sibling's engagement in family future planning (e.g., family made an appointment with a special needs lawyer).
2. **Adult with ASD: Quality of Life (T1 & T3). Proxy report**: Siblings will rate their brother/sister's quality of life using the Life Experiences Checklist. This has been used as a proxy-report measure by family members and support staff to rate the QOL of adult with ASD. Five sections cover the individual's home environment, leisure activities, relationships, freedom, and opportunities. **Self-report**: Adults with ASD will complete the WHOQOL-BREF, a shorter version of World Health Organization Quality of Life assessment, the WHOQOL-100, which includes 26 items rated on a 5-point scale addressing physical and psychological health, social relationships, and environment. This measure has been used with adults with ASD, including [name] collaborative study with [name]. We will modify administration as described by Hong and colleagues to ensure greater accessibility across the autism spectrum.
3. **Adult with ASD: Unmet Needs**. Adults with ASD will report on their perceptions of unmet needs using items that Nicolaidis and colleagues adapted for adults with ASD using items from the 2002/ 2003 Joint US Canada Survey and 2007 National Health Interview Survey Questionnaire—Adult Access to Health Care and Utilization. They will report on unmet needs in medical care, mental healthcare or counseling, preventive services, emergency department visits, outpatient visits, and hospitalizations. In collaboration with the CAB, we will add items probing unmet needs in residential and occupational domains.
4. **Adult with ASD: Perceptions of Family Relationships**: Adults with ASD will complete the 11-item Family subscale of the Social and Emotional Loneliness Scale for Adults (e.g., "No one in my family cares about me," "I wish my family were more concerned about my welfare"). This scale has adequate reliability and validity and has been used in adults with ASD.

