## **APPROACH**

### **Overview**

The goal of the proposed research is to develop and evaluate the Siblings FORWARD program using behavioral telehealth technology. First, we aim to develop the 6-session Siblings FORWARD program in collaboration with community organizations. Siblings, adults with ASD, and community providers will give feedback on the proposed program through focus groups and/or individual interviews. Second, feasibility of the Siblings FORWARD program will be evaluated through an open trial (N=5 families). We will assess recruitment capability, appropriateness of outcome measures, program acceptability, and viability of the procedures. Finally, we will conduct a pilot randomized controlled trial (RCT) (N=36 families) to examine effects on the proposed targets and whether sibling involvement led to the creation of a plan of action for future planning.

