RCT. The final phase of the proposed project will implement an RCT to examine whether the program is feasible and associated with improvements in the treatment targets (see Measures and Figure 1). Thirty-six siblings will be recruited and randomly assigned to participate in Siblings FORWARD (N=18) or receive written materials about future planning (N=18). Siblings assigned to Siblings FORWARD will complete Time 1 (pre-program) measures, participate in the 6-session intervention over 4 months, complete Time 2 measures immediately after program completion, and complete Time 3 measures 3 months later. Those assigned to the control condition will complete Time 1 measures at the time of enrollment, Time 2 measures 4 months after enrollment, and Time 3 measures 7 months after enrollment. With the exception of the clinician rating of the sibling's ASD symptoms (see Measures), all data will be collected by the Boston University study team via home visits in order to separate data collection from the Arc providers. Adults with ADS and their families will determine whether the adult with ASD can complete the questionnaires (see Methods). When possible, the adult with ASD will complete the measures independently in the presence of a Boston University research team member. These measures can also be completed with the support of a research team member, sibling, parent, or service provider. Given possible geographic separation, sibling data will be collected via mailed questionnaire packets. We will track this data collection method to inform future data collection logistics.

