## Siblings FORWARD Program Description

The goal of the Siblings FORWARD program is to increase siblings' skills, knowledge, and self-efficacy to enable them to assume a greater role in future planning for their brother/sister with ASD. Program completion is expected to be associated with a higher likelihood of developing and implementing a future plan of action that includes short- and long-term planning goals. In turn, improved future planning is expected to be associated with longer-term improvements in unmet needs, quality of life, and family relationships for the adult with ASD (Figure 1). The Siblings FORWARD program will be delivered in six sessions over a 4-month period. Siblings will participate in all interactive online sessions guided by an Arc family support staff member; the adult with ASD will participate in one session, when possible. To increase future uptake and scalability, the program will be delivered by community providers with expertise in serving adults with ASD and their families. Sessions will equip sibling participants with concrete skills necessary to actively engage in future planning. Sessions follow a deliberate sequence starting with assessment of siblings' current involvement and skills and motivational interviewing techniques to bolster siblings' motivation for future planning; followed by instruction on skills related to communication and problem-solving, education about existing services and systems; application of problem-solving and communication skills to their plan of action; incorporation of the adult with ASD into the planning process; and final application of skills to the creation of a document outlining concrete next steps for the sibling's involvement in future planning. Content is outlined in Table 3 and Appendix 2.

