*Aim 3: To assess the outcomes of participation in the Siblings FORWARD program.* We will examine whether the program shows promise of being successful with the intended population by conducting two-way repeated measures ANOVAs examining main effects of intervention condition (Siblings FORWARD vs. control) and repeated for assessment (pre- post- and 3-month follow up) on measures for program targets (sibling problem solving skills, family communication, future planning self-efficacy, barriers to future planning, and knowledge of services and family future plans) and proximal outcomes (sibling plan of action and adult with ASD quality of life, perceptions of unmet needs, and family relationships). Post-hoc tests will be used in multiple comparisons between groups and within each group. Effect sizes (Cohen's d) will be calculated using the mean difference of the changes recorded from pre- to post-program. We will also analyze percent change and reliable change. If data are missing, analyses will be performed using the 'last observation carried forward' method for intention-to-treat analysis. We will examine descriptive statistics (mean, SD, confidence intervals) at the participant level for patterns and direction of change on outcome measures. We will conduct intent-to-treat analyses if there is program attrition. Finally, we will examine benefit of the program to control participants who elect to participate in the Siblings FORWARD program using one-way ANOVAs (pre to post-program) on treatment targets and proximal outcomes.

We will conduct a preliminary investigation of potential moderators of program effectiveness, including characteristics of the sibling (BAP), family (income, race/ethnicity, English as the primary language, number of family members with ASD), and adult with ASD (severity of ASD symptoms, problem behaviors, functional independence). We will calculate correlations between these variables and change scores in primary outcome variables, and independent samples t-tests between these variables and program completion status.

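### Plan creation cannot be tested when controls are given the same plan template at Time 2, and no route is set for collecting plans from program siblings who stop early

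*Combined protocol and SAP*

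**What the plan says.** **The aim.** Under Approach, Overview, one of the two things the pilot RCT is to examine is "whether sibling involvement led to the creation of a plan of action for future planning". The Siblings FORWARD Program Description points the same way: "Program completion is expected to be associated with a higher likelihood of developing and implementing a future plan of action".

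**The measurement.** Under Measures, Proximal Outcomes, the first item covers the plan itself, with T2 as its time point, and states: "Siblings will submit a written plan of action at the final session; control participants will complete this plan at Time 2". Both arms use a template. The item goes on: "Researchers will rate each plan according to the following criteria", followed by five criteria (goals and next steps, scope, alignment, accuracy, detail). It adds for the 3-month follow-up: "we will assess whether or not the sibling attempted or achieved their primary short-term goal".

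**Timing and collection.** Under Procedures, RCT, 18 siblings are allocated to each arm. Program-arm Time 2 follows completion of the program; control Time 2 falls 4 months after enrollment. Siblings return their data by post.

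**Analysis.** Data Analysis, Aim 3, lists the plan of action among the proximal outcomes for a two-way repeated measures ANOVA and commits to intention-to-treat. On missing values it says: "If data are missing, analyses will be performed using the 'last observation carried forward' method for intention-to-treat analysis".

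**The concern.** Two things do not fit together.

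1. The aim is about whether a plan comes into being. In the control arm the trial itself brings one into being, by asking for it at Time 2. In the program arm a plan is submitted at Session 6. Whether a plan exists then shows who attended the last session and who posted back a form. It does not show whether the program leads siblings to plan.
2. The rating of plan quality does not have the first problem, but it has another. A program sibling who stops before Session 6 has no stated point at which a plan is collected, and no Time 2 date either. The rating would then be available for program completers and for controls who respond, and those are not the groups that were randomized. If early stoppers are the less engaged siblings, leaving them out flatters the program.

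At stake are a named objective that cannot be answered as measured, and a comparison of plan quality exposed to selection.

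**Working it through.** The documents give no power calculation, dropout rate, plan-creation rate or rating range, so there is no stated figure to reproduce. The only fixed input is 18 siblings per arm (Procedures, RCT). Every rate, effect size and rating below is an assumption, shown over a range.

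**Step 1. Plan existence.** Difference = (program plans)/18 - (control plans)/18, with Fisher's exact test.

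| Program | Control | Difference | p |
|---|---|---|---|
| 18/18 | 18/18 | 0 points | 1.00 |
| 16/18 | 18/18 | -11 points | 0.49 |
| 14/18 | 18/18 | -22 points | 0.10 |
| 13/18 | 18/18 | -28 points | 0.045 |
| 16/18 | 12/18 | +22 points | 0.23 |
| 18/18 | 14/18 | +22 points | 0.10 |
| 18/18 | 12/18 | +33 points | 0.019 |

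With full control return the difference is capped at zero, however well the program works. With incomplete control return it can be positive, even nominally significant. Both signs come from attendance and postal return, so neither speaks to the aim.

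**Step 2. Who is in the rating.** Set the sections side by side:
- The outcome definition ties the program plan to the final session.
- Procedures ties program-arm Time 2 to finishing the program.
- Neither says what happens to a sibling who stops early.
- Aim 3 offers LOCF, but the plan is rated only at T2. Table 3 has a preliminary draft made in Session 1, but no rating of it is planned and controls have no counterpart.
- A repeated measures ANOVA also does not fit an outcome scored once.

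So LOCF supplies no value, and the default analysis set is completers against responding controls. The 3-month item is affected too: it refers to the sibling's primary short-term goal, which someone without a final plan may not have.

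**Step 3. Size of the selection.** If a share q of the program arm is left out, the completer mean differs from the full-arm mean by q x (completer mean - non-completer mean). With an assumed 4 of 18 stopping early, q = 4/18 = 0.22, so 22% of the gap between the two subgroups enters the treatment contrast.

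**Step 4. How much the missing rule matters.** Suppose the lowest score is 0, program completers average 7, controls average 5 and all controls respond. Difference = 7 x (18 - k)/18 - 5 when k early stoppers are scored 0:
- k = 0: 7 - 5 = +2.00
- k = 4: 7 x 14/18 - 5 = +0.44
- k = 6: 7 x 12/18 - 5 = -0.33

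The break-even dropout is 1 - 5/7 = 29%. For means of 6 vs 5 it is 1 - 5/6 = 17%; for 8 vs 5, 1 - 5/8 = 38%. The sign can turn on a rule the plan does not state.

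**Step 5. Can the rating favor the program?** Yes. Power for a two-sided t-test at an assumed 0.05, from the noncentral t with noncentrality d x sqrt(n1 x n2/(n1 + n2)): at d = 0.8, 18 vs 18 gives 0.8 x 3 = 2.40 and power 0.65; 14 vs 18 gives 0.8 x 2.81 = 2.24 and power 0.58. At d = 1.0 the powers are 0.83 and 0.78.

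**The case against.** The best defense is that the protocol does not define the outcome as the mere existence of a plan. It defines a five-criterion rating and a 3-month assessment of goal attainment, and Aim 3 names no analysis of creation rates. Giving controls the same template is what makes a rating comparison possible at all. This is also a pilot that sets out to describe retention, and Aim 3 promises intention-to-treat if there is attrition.

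Much of this stands, and it rules out two stronger readings that a reader might infer:

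- *That the plan comparison can only be null or favor control.* This holds for plan existence alone, and only if every control returns the template. Postal collection does not guarantee that, and Step 1 shows positive differences once some controls do not respond. The rating and goal outcomes can favor the program (Step 5). Its plans are also written with a provider and a shared desktop, help that the outcome definition does not mention for controls.
- *That program dropouts never submit a plan.* The documents do not say so. They set no rule for early stoppers, and a draft exists from Session 1. Nor is loss confined to the program arm, since controls may fail to reply.

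What the defense does not answer is that the stated aim is still creation, and that an intention-to-treat promise resting on LOCF cannot be kept for an outcome with no earlier rated value.

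**Conclusion.** The point holds in a limited form. Plan existence cannot test the Overview's aim, because the control arm's plans are elicited by the study. With full control return the difference is bounded above by zero: 0 points at full attendance, -22 points at an assumed 14/18. The rated-quality and goal outcomes are usable and can go either way, but as written the rating sets program completers against responding controls. With an assumed 4 of 18 stopping early, 22% of the program arm is missing from that rating.

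The mismatch between aim and measurement, and the lack of anything for LOCF to carry forward, follow from the text alone. The sizes rest on assumed attendance, return and ratings. This should be corrected before the RCT starts, but it is repairable and does not invalidate the outcome.

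**What to change.** 1. Collect the plan template from all randomized siblings at a common Time 2, 4 months after enrollment as already set for controls, including program siblings who stopped early.
2. Restate the RCT aim as rated plan quality and 3-month goal attainment, so that the Overview agrees with the outcome definition.
3. If creation is still to be tested, ask both arms the same question, placed before the template, about plans written apart from any study form or session. Report Session 6 plans separately. Counting them as creation in the program arm only would introduce the opposite asymmetry.
4. Analyze the T2-only rating as a between-group comparison, without LOCF and outside the repeated measures ANOVA. Score unreturned plans in either arm as lowest only in a stated sensitivity analysis, because Step 4 shows that this rule alone can reverse the sign.

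Cost: one mailing to early stoppers, one questionnaire item if creation is kept, and a few sentences of text. The program-arm mean will probably be less favorable once early stoppers are included.

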***Application to Current Proposal:*** Common barriers to sibling involvement in future planning include geographical separation from the individual with ASD and/or parents and the sibling's concurrent midlife demands (e.g., responsibilities to children, spouse, aging parents, or employer). The application of VTC technology will directly address these barriers and increase accessibility and program engagement. Most sessions will be delivered in a one-on-one format between the provider (in his/her office) and sibling participant (at home). In addition to audio and video streams, the VTC platform offers a shared desktop function in which both the provider and the sibling can view and edit documents in real time and access the documents between sessions to reinforce skills. This shared desktop function will be used to create program documents (e.g., the sibling plan of action). When the adult with ASD participates in session, families will have the choice of having the sibling and adult in the same room or setting up a 3-way VTC session. Finally, the ease of video recording will facilitate close consultation between the PIs and the service providers delivering the program.

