#### Program Targets: Sibling Future Planning Knowledge & Skills (Measured at Time 1, Time 2, & Time 3)

1. Problem Solving Skills. Siblings will complete the Social Problem-Solving Skills Inventory-Revised (SPSI-R). This 52-item self-report measure was used in a problem-solving intervention with mothers of children with ASD. Five dimensions assess how the individual strategically approaches a situation (positive problem orientation, negative problem orientation, rational problem solving, impulsivity carelessness style, and avoidance style). Siblings will rate the extent to which each item is 1 (not at all true) to 5 (extremely true) of them. Higher scores indicate better problem-solving skills. Good reliability is reported.
2. Family Communication about Future Planning. Siblings will rate the frequency with which they have had family discussions about planning for the future of their brother/sister with ASD. Siblings will respond to a 1-item measure previously used in a study evaluating a peer-support program for aging caregivers of adults with intellectual and developmental disabilities. The item is scored on a 3-point scale (not discussed at all, discussed somewhat, discussed a great deal).
3. Future Planning Self-Efficacy. We will adapt the Caregiving Self-Efficacy Scale that has been used by with parents and adult siblings to evaluate participation in a peer-support intervention for aging caregivers. The scale consists of 6 items rated on a 4-point scale (strongly disagree to strong agree). Sample items include: I honestly believe I can be a good caregiver to my relative; If anyone can find the answer to what is troubling my relative, I can. The scale has good reported reliability (alphas .73-.82).
4. Sibling Barriers to Future Planning. Siblings will complete a list of barriers to future planning adapted from a measure used by Heller and Caldwell. The original list included 12 barriers such as: difficulty finding helpful contact persons within the service system, emotional barriers involved with thinking their parents' mortality, or disagreement with a relative with a disability about the future.
5. Knowledge of adult services and delivery systems. Siblings will rate their knowledge of the services received or needed by their brother/sister with ASD. We will use a list of 12 adult services: physical

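### The sibling-rated quality-of-life checklist mixes a change in the rater with a change in the adult, so it should not carry the between-arm quality-of-life comparison

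*Combined protocol and SAP*

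**What the plan says.** **The rating.** Under Measures, Proximal Outcomes, item 2, the sibling rates the adult's "quality of life using the Life Experiences Checklist", at T1 and T3. On content: "Five sections cover the individual's home environment, leisure activities, relationships, freedom, and opportunities". On earlier use: "This has been used as a proxy-report measure by family members and support staff". The same item adds the WHOQOL-BREF as the adult's self-report, with administration adapted for accessibility.

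**The rater.** Procedures (RCT) makes the sibling the randomised person, 18 per arm. The arms are a six-session program or written materials, so the sibling cannot be blind to allocation.

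**What happens to the rater.** The Siblings FORWARD Program Description gives raising the sibling's knowledge as part of the program's goal. In Table 3, Session 1 asks the sibling to find out what plans the family already has. Session 2 sets goals for talking with relatives, Session 3 covers service systems, and Session 5 brings in the adult where possible. Program Targets, item 5, measures what the sibling knows: "Siblings will rate their knowledge of the services received or needed by their brother/sister with ASD". Item 6 does the same for the family's plans. Under Control Condition, controls get the same written materials that Session 3 hands out and no sessions until outcome data are complete.

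**Limits on the self-report.** Under Sample & Recruitment, adults complete self-report measures only if capable. Procedures (RCT) lists the sibling among those who may help.

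**The analysis.** Data Analysis, Aim 3, compares quality of life by arm with repeated-measures ANOVA and takes Cohen's d from pre-to-post changes.

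**The concern.** A proxy rating measures the adult through what the proxy knows and believes. Here the proxy is the treated person, and part of the treatment's purpose is to alter what that person knows and how much contact with the family that person has. Randomisation makes the T1 ratings comparable between arms. It does not protect against a change in the rater that the treatment itself causes.

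The protocol expects knowledge gaps at the start. Its service and family-plan measures provide for siblings who do not know, and it states: "Common barriers to sibling involvement in future planning include geographical separation from the individual with ASD". No corresponding handling of unknown items is described for the checklist.

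The protocol's causal order adds to the difficulty. The Program Description places quality-of-life gains in the longer term, after planning has improved, yet the checklist is listed as a proximal outcome and tested at three months. Sibling knowledge, a direct target, should move first.

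What is at stake is how one result is read. An apparent effect on the adult could be carried as an effect size into the larger-trial application in Table 4. Equally, a true benefit could be missed.

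**Working it through.** **1. Structure.** In each arm, the mean T1-to-T3 change in the checklist is the true change in the adult plus the change due to the rater. Subtracting arms:

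observed difference = (true change, program − true change, control) + (rater change, program − rater change, control).

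The second bracket is zero only if raters change equally in both arms. The program is designed to make them differ. The sibling checklist supplies one contrast for two unknowns. Aim 3 describes no rater outside the randomised pair of arms and no analysis of proxy-self agreement.

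**2. What can be checked from the plan.** Arm sizes add up: 18 + 18 = 36 under Procedures, and 24 + 12 = 36 in Table 4. The documents give no alpha, power, effect size or SD, so the 36 cannot be derived from a power calculation. They also give nothing from which to estimate the rater change.

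**3. Illustration: how sensitive is a trial of this size?** Assumed: two-sided 0.05, all 36 analysed, equal variances, two-sample t test.

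- Detectable difference at 80% power, normal approximation: (1.960 + 0.842) × √(2/18) = 2.802 × 0.333 = 0.93 SD. With the t distribution it is 0.96 SD.
- Rejection rate for a net shift δ: noncentral t, df = 34, noncentrality δ × √(18/2) = 3δ.

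Suppose the adult does not change and only the rater shifts, by δ SD of the analysed score:

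| Assumed shift δ | 3δ | Chance of p<0.05 |
|---|---|---|
| 0 | 0 | 5% |
| 0.2 | 0.6 | 9% |
| 0.3 | 0.9 | 14% |
| 0.5 | 1.5 | 31% |
| 0.8 | 2.4 | 65% |

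If δ is in SDs of the raw score and change scores are analysed with an assumed T1–T3 correlation of 0.7, the change SD is √(2 × (1 − 0.7)) = 0.775 raw SD. Dividing each shift by 0.775 raises the rates for 0.2, 0.3, 0.5 and 0.8 to about 12%, 20%, 47% and 85%.

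**4. The same table read for masking.** Take an assumed true benefit of 0.5 SD. With no rater shift, the chance of p<0.05 is 31%. A rater shift of −0.3 leaves a net 0.2 and the chance falls to 9%. A shift of +0.3 gives a net 0.8 and the chance rises to 65%. The documents do not say which sign to expect.

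**5. Precision of the self-report comparison.** The number of capable adults is not given. If 9 or 12 per arm could self-report (assumed), the detectable difference at 80% power (t) is 1.41 or 1.20 SD, against 0.96 SD with all 18.

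**The case against.** The strongest reply is that this is one of many outcomes in a 36-family pilot that asks only whether the program shows promise, that the plan already pairs the proxy with a self-report, and that family members are established raters of this checklist. Knowledge of assignment affects every sibling-reported measure, not only this one. All of that is true. It limits the point to how one result is interpreted. It does not remove the point, because the self-report is restricted to capable adults, may be completed with the randomised sibling's help, and is not given priority over the proxy in Aim 3.

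Several stronger readings are tempting, and the documents do not support them:

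- **That the program teaches the sibling about the adult's daily life.** Sessions cover communication, service systems, problem-solving, family plans and the adult's preferences. Learning about home or leisure would be indirect, through family contact and Session 5, which can proceed without the adult.
- **That only the program arm's raters change.** Controls receive the same written materials and complete a plan of action at Time 2, before the T3 rating. The arms differ in degree.
- **That the checklist simply re-measures sibling knowledge.** The knowledge targets concern 12 services and items such as a will, a trust and guardianship. Overlap with the five checklist areas is small.
- **That the bias favours the program.** This follows only if siblings score unknown items as absent. An informed sibling may also rate lower.
- **That most siblings live apart from the adult.** Separation is called a common barrier, but no share is given, and recruitment is mainly through two local Arc chapters and a state sibling network.

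**Conclusion.** The concern holds as a limit on interpretation. The checklist is rated by an unblinded, randomised sibling whose knowledge and contact the program aims to raise more than the control condition does. The planned comparison cannot tell a changed rater from a changed adult. This rests on the documents alone.

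The size and direction of the rater component are unknown. The rejection rates of 9% to 65% for shifts of 0.2 to 0.8 SD show what such shifts would do with 18 per arm; they do not estimate what will happen. They depend on the assumed shifts, full follow-up and equal variances.

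A reader might infer that the trial's quality-of-life evidence is worthless, or biased towards benefit. Neither follows: a self-report is already collected, and masking is as possible as inflation. The matter calls for an inexpensive improvement to one outcome; it is not a defect of the trial as a whole.

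**What to change.** 1. In Measures (Proximal Outcomes, item 2) and Data Analysis (Aim 3), name the adult's WHOQOL-BREF, change from T1 to T3, as the between-arm quality-of-life comparison where the adult can self-report. Stating T1 to T3 also settles a mismatch: Aim 3 refers to pre, post and follow-up assessments and takes effect sizes from pre to post, but quality of life is not measured at T2.
2. In Procedures (RCT), require that any help with completing the WHOQOL-BREF comes from someone other than the randomised sibling, such as the research team member already listed there.
3. Report the Life Experiences Checklist by arm as exploratory, sibling-perceived quality of life, and not as evidence of an effect on the adult.
4. Where both measures exist, show proxy-self agreement by arm.

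**Cost.** Text changes, one restriction on who may help, and one descriptive table. No new data are collected. The comparison loses precision because fewer adults contribute, and it says nothing about adults who cannot self-report.

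Two other remedies might suggest themselves, and neither is recommended. A parent or staff rater is an informant class the RCT does not plan to enrol. Parents are also drawn into the program's family conversations, and Arc staff raters would undo the separation of data collection from Arc providers. Scoring only items the sibling knows at both visits conditions on knowledge after randomisation, which the program is meant to change, and could introduce a new bias.
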